2.8.1.5 Adverse events of special interest / grouping of AEs

Groupings of AEs of special interest consist of adverse events for which there is a specific clinical interest in connection with LCI699 treatment (i.e. where LCI699 may influence a common mechanism of action responsible for triggering them) or adverse events which are similar in nature (although not identical). The list of AESIs is updated periodically after MedDRA update and/or review of accumulating trial data, and stored on the eCRS platform. The results for the Final CSR will use the list in place at the time of DBL.

2.8.1.6 Adverse events by time of onset

AEs will also be categorized by the time of onset, and separate summaries shown for defined time periods of the study.

The time periods used will be

- Baseline to Week 26
- Week 26 to Week 48
- Week 48 to Week 72
- Week 72 onwards

The denominator for each time period will be the number of patients still on the study at the start of that period. These summaries will be reported for

- Adverse events of Special Interest, regardless of study drug relationship, by category and preferred term
- Adverse events of Special Interest with suspected study drug relationship, by category and preferred term

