WHO	World Health Organization

1 Introduction

The SAP document describes the planned statistical analyses for the Final CSR of study LCI699C2301 in the treatment of Cushing's disease. It incorporates analysis of the long-term safety and efficacy of the study, including data collected during both the core phase (up to Week 48) and the optional extension period. The optional extension period will end 16 months after all patients have completed Week 72 or discontinued early (prior to Week 72).

The analysis will be performed after all patients have completed the extension period or discontinued earlier.

The analysis of the core phase, including the results of the primary and key secondary outcomes was detailed in the CSR written following the DBL which occurred once all patients had completed the core phase or discontinued earlier. These details of these analyses can be found in the corresponding SAP, with cover date 06-Jul-2018.

After the interim CSR was published, additional protocol deviations were reported which affect the per-protocol populations used to perform the per-protocol analyses of the primary and key-secondary endpoints, therefore the Final CSR will report the updated results of these per-protocol analyses.

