1.2.5 Optional extension period

Patients who continue to receive clinical benefit, as assessed by the study investigator and who wish to enter the extension period must be re-consented at week 48. Patients who enter the extension period will do so without interruption of study drug or assessments. The optional extension period will end after all patients have completed Week 72 or have discontinued early (prior to Week 72).

Study CLCI699C2301 ends when all ongoing patients have transitioned to the long-term safety follow-up study or have been offered local alternative treatment options; this period will not exceed 4 months after all ongoing patients have completed Week 72. Patients who continue to benefit from treatment and have completed Week 72 will be offered participation in a separate long-term safety follow-up study after the database lock of the core phase is completed.

If the long-term safety follow-up study is opened at site, patients should transition to the long-term safety follow-up study. If this option is not available, the patient can either be offered a local alternative treatment option or stay in the study until the study end (i.e. 4 months after the last patient completes Week 72) Patients entering the long-term safety follow-up study will complete an EOT visit. For these patients, the EOS visit is not applicable, as treatment on LCI699 will not be interrupted. Patients not entering the long-term safety follow-up study will complete an EOT visit, and an EOS visit 30 days after the last dose administration.

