2.1.1.7 Calculation of proportions of responders

All enrolled patients will be included in the analysis for calculating the proportion of responders at time points up to Week 48.

For calculation of proportion of responders beyond Week 48 (e.g. a time point in extension period), the following rules will be applied to determine whether patients are included in the analysis.

1) patients who declined to enter optional extension period after completion of the core phase will always be excluded.

2) patients who discontinued prior to the data cutoff date for the Final DBL will be included up to the furthest scheduled visit they could have completed if they had not discontinued early based on data cut off and last completed based on the date of last completed schedule visit and analyses cut-off date. For example, if the last completed scheduled visit for an early discontinued patient is Week 52, and the time between data cutoff and last completed scheduled visit is 8 weeks, he/she will be included in the analyses up to Week 60.

If included in the analysis for calculating the proportion of responders at a given timepoint, patients who discontinued before this timepoint will be counted as non-responders.

Patients randomized to placebo during the RW period, will not be included in the denominator for visits at which they received placebo.

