2.1.1.10 Criteria of adequate follow-up for time points in the extension period

For a given time point in the extension period, it will be considered to have adequate follow-up to be included in the reporting activities if there are at least 15 patients available for the analysis at that time point.

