2.4 Treatments (study treatment, rescue medication, concomitant therapies, compliance)

2.4.1 Study treatment / compliance

In the Final CSR the exposure to the study drug will be summarized for the overall study period only, using the SAS.

Duration of exposure

• For overall study period, duration of exposure to LCI699 for patients in the SAS is calculated as below:

•for Placebo group:

Duration of exposure (weeks) = (min (date of last administration of study medication, date of data cut-off, date of death) – date of first administration of LCI699 + 1)/7 – Duration of exposure to Placebo

•for LCI group and non-randomized patients

Duration of exposure (weeks) = (min (date of last administration of LCI699, date of data cut-off, date of death) – date of first administration of LCI699 + 1)/7

The above duration calculation includes the periods of temporary interruption.

Dose reduction/interruption

The number of patient who has at least one dose reductions or interruptions, and the corresponding reasons will be summarized by study period. Although patients may have multiple dose reduction or interruption with the same reason, patient will be counted only once for each distinct reason.

The actual and planned doses administered and reason for dose change will be listed with UFC information.

Dose of LCI699

The LCI699 average total daily dose by visit during the overall study period will be summarized using descriptive statistics and displayed graphically. Dose levels whilst on placebo, for patients randomized to placebo during the RW period, will not be included in the calculations.

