2.8.1.3 General rules for AE reporting

AE summaries will include all AEs starting on or after study day 1 (i.e. on or after the day of the first administration of study drug) but no later than AE summary cutoff defined in Section [2.1.1.9](#). All AEs before data cutoff date will be listed, including those that start before study day 1. AEs starting prior to study day 1 will be identifiable based on the AE start date displayed in the listings.

AEs will be summarized by presenting the number and percentage of patients having at least one AE, and having at least one AE in each body system/primary system organ class and for each preferred term using the most current MedDRA coding available prior to database lock. A subject with multiple occurrences of an AE will be counted only once in the AE category.

Separate AE summaries will be presented by primary system organ class, preferred term, and maximum CTC grade. A patient with multiple CTC grades for an AE will be summarized under the maximum CTC grade recorded for the event. In the summaries presented by grade, all AEs will be pooled regardless of whether they are CTC gradable or not. AEs with missing CTC grade will be summarized under “missing”.

The frequency of CTC grades 3 and 4 AEs will be summarized separately.

Any information collected (e.g. CTC grades, relationship to study drug, action taken etc.) will be listed as appropriate.

Adverse events with a start date which corresponds to when a patient was receiving placebo will not be included in adverse event summaries.

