2.8.4.2 Vital signs

All vital signs data (weight (kg), body temperature ($^{\circ}$ C), pulse rate (beats per minute), and systolic/diastolic blood pressure (mmHg)) will be listed by patient and visit/time, and abnormalities will be flagged on listing. Shift table based on notable value will be provided for vital signs. For blood pressure, triplicate measurements are planned when assessed, and the mean of available values will be taken for analysis purposes. Change over time from baseline will be summarized.

The criteria for clinically notable abnormalities are defined as follows:

Clinically notable elevated values

- Systolic BP: ≥ 180 mmHg and an increase ≥ 20 mmHg from baseline
- Diastolic BP: ≥ 105 mmHg and an increase ≥ 15 mmHg from baseline.
- Pulse: ≥ 120 bpm with increase from baseline ≥ 15 bpm
- Weight: Increase from baseline of $\geq 10\%$
- Temperature: Increase from baseline of $\geq 39.1^{\circ}$ C

Clinically notable below normal values

- Systolic BP: ≤ 90 mmHg and a decrease ≥ 20 mmHg from baseline
- Diastolic BP: ≤ 50 mmHg and a decrease ≥ 15 mmHg from baseline
- Pulse: ≤ 50 bpm with decrease from baseline ≥ 15 bpm
- Weight: Decrease from baseline of $\geq 5\%$

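### The AESI-by-onset percentages compare windows of very unequal length and ignore placebo time; separately, the notable-high temperature rule cannot be met as written

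*SAP*

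**What the plan says.** SAP 2.8.1.6 plans two AESI summaries by time of onset, one regardless of drug relationship and one for suspected events. The windows are Baseline to Week 26, Weeks 26 to 48, Weeks 48 to 72, and Week 72 with no upper limit. The percentage base is a headcount: "The denominator for each time period will be the number of patients still on the study at the start of that period".

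The numerator follows SAP 2.8.1.3: "Adverse events with a start date which corresponds to when a patient was receiving placebo will not be included in adverse event summaries". SAP 2.8 pools both randomized arms into one column beside Non-randomized and All patients.

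Placebo time is handled differently elsewhere in the SAP. For response rates, SAP 2.1.1.7 states: "Patients randomized to placebo during the RW period, will not be included in the denominator for visits at which they received placebo". SAP 2.4.1 subtracts placebo duration from LCI699 exposure, but gives one total only: "In the Final CSR the exposure to the study drug will be summarized for the overall study period only, using the SAS".

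The SAP gives two end dates. Section 1: "The optional extension period will end 16 months after all patients have completed Week 72" (or discontinued before it). Section 1.2.5 ends the extension once all patients have completed Week 72 or left, and says of the study's end: "this period will not exceed 4 months after all ongoing patients have completed Week 72".

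In SAP 2.8.4.2, the notable-high entry for temperature begins "Temperature: Increase from baseline of" and continues with a limit of at least 39.1 °C.

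**The concern.** A table by time of onset exists to show whether risk changes over time, so its four percentages will be read across. A percentage with at least one event depends on how long patients are watched. With no upper limit on the last window and no exposure by window, a constant or falling risk can look like a late rise. For AESIs such as pituitary tumor enlargement or QT prolongation, that would look like a safety signal.

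In Weeks 26 to 48 the error runs the other way. Placebo patients count fully in the denominator, while events that start on placebo are removed from the numerator.

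The temperature rule is a separate defect in another section. Programmed literally, its shift category and listing flag would be empty because of the wording, and a reader could take that to mean no patient had a high temperature.

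**Working it through.** The SAP states no rate for these tables, so there is no figure of its own to reproduce.

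**Window lengths.** From the visit days in SAP 2.1.1.3 (Days 1, 183, 337, 505), the first three windows are 182/7 = 26, 154/7 = 22 and 168/7 = 24 weeks.

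**Potential length of the last window.** Enrollment finished on 22-Mar-2017 (protocol, Amendments 4 and 5). Taking that as the last first dose, that patient's Week 72 is 504 days later, 8-Aug-2018. Sixteen months on is 8-Dec-2019; four months on is 8-Dec-2018.

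| Patient | 16-month text | 4-month text |
|---|---|---|
| First dose 22-Mar-2017 | 69.6 weeks | 17.4 weeks |
| First dose 2-Mar-2015 | 176.9 weeks | 124.7 weeks |

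Only about 12 patients had been treated by 2-Mar-2015 (protocol, Amendment 2; the SAP says 10).

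**Effect of length for one patient.** The documents give no AESI hazard, so three constant hazards λ are assumed: -ln(0.9)/24, -ln(0.8)/24 and -ln(0.7)/26 per week. The chance of at least one event in w weeks is 1 - exp(-λw).

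| Assumed hazard | 26 wk | 22 wk | 24 wk | 69.6 wk |
|---|---|---|---|---|
| 10% per 24 wk | 10.8% | 9.2% | 10.0% | 26.3% |
| 20% per 24 wk | 21.5% | 18.5% | 20.0% | 47.6% |
| 30% per 26 wk | 30.0% | 26.1% | 28.1% | 61.5% |

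**Effect on the whole column.** Accrual follows the amendment status dates: 12 patients at 2-Mar-2015, 63 spread evenly to 1-Mar-2016 (total 75), and 62 to 22-Mar-2017 (total 137). A constant exit rate μ is set so that 91 remain on 25-Jun-2018 (Amendment 5), giving μ = 0.00333 per week, about 16% per year. With potential follow-up f in the window, the expected proportion is the mean over patients of λ/(λ+μ) × [1 - exp(-(λ+μ)f)].

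| Assumed hazard | First three columns | Last, 16 months | Last, 4 months | Last, 16 months, hazard halved |
|---|---|---|---|---|
| 10% per 24 wk | 9-10% | 35.1% | 24.3% | 19.9% |
| 20% per 24 wk | 18-21% | 57.8% | 43.0% | 36.6% |
| 30% per 26 wk | 25-29% | 69.9% | 54.8% | 48.1% |

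**Placebo time.** SAP 3.1 plans 33 patients per arm. A placebo patient who completes the period has 22 - 8 = 14 weeks at risk on LCI699. With 132 patients in the denominator, the Weeks 26-48 figure is [99(1 - exp(-22λ)) + 33(1 - exp(-14λ))]/132. At the two higher hazards:

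| Case | 20% per 24 wk | 30% per 26 wk |
|---|---|---|
| No placebo time | 18.5% | 26.1% |
| All patients, 8 weeks on placebo | 16.9% | 23.9% |
| Randomized column, 8 weeks on placebo | 15.4% | 21.8% |
| All patients, 2 weeks on placebo | 18.1% | 25.5% |

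**Temperature.** A baseline of 37 °C would need 37 + 39.1 = 76.1 °C to be flagged.

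**The case against.** Each planned percentage is valid as a conditional proportion, its denominator is stated, and no test or trend statement is planned. That is correct. The fault lies in setting such proportions side by side over unequal windows with nothing to correct the reading.

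SAP 2.1.1.9 closes each patient's AE time at the data cut-off or, if earlier, at the later of last dose plus 30 days and the safety follow-up visit. That caps individual time but does not equalize it.

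The strongest objection is to size. Protocol 4.1.5 and 6.1.5 ask patients to move to the follow-up study, or to a local alternative, within 2 months of its becoming available. The exit rate was fitted at a date when Amendment 5 was still waiting for that study, so it probably contains few transfers, and the 16-month figures are near the upper end. Capping the last window at 40 weeks in the same model gives 15%, 29% or 40%; a 26-week cap gives 10%, 21% or 29%, level with the first window. The 26-week case is implausible: 91 patients were still in the study on 25-Jun-2018, when median potential time past Week 72 was already about a year under the accrual above. The direction stands; the exact size does not.

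The placebo point is small if patients are rescued early. Protocol 1.2.1.2.2 reports mean mUFC at 4 times ULN two weeks after withdrawal in the earlier study, and the 2-week case moves the figure by about half a percentage point. These patients also return to LCI699 within the window, so dropping them from the denominator would be wrong too. Patient-time handles both.

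The two end-of-study statements and the temperature line are text corrections, and the temperature line is unrelated to the onset tables. Both still need correcting before tables are run.

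**Conclusion.** The concern holds. The last AESI-by-onset column is not comparable with the other three. Under the 16-month text and the assumed hazards it reads roughly two and a half to three and a half times as high with no change in risk, and it still rises if the risk halves. This rests on constant hazards that the documents do not supply, enrollment dates taken as first-dose dates, even accrual between reported counts, and an exit rate that does not speed up after June 2018.

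The placebo mismatch is real but modest: at most about 2 percentage points for all patients and about 3 to 4 in the Randomized column at the two higher hazards. It assumes 33 placebo patients and no dropout by Week 26.

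The temperature rule is wrong as written. Pyrexia AEs, temperature listings and change-from-baseline summaries are untouched, as are the overall AE and AESI tables and the primary and key secondary inference. These changes should be made; none threatens the trial's main conclusions.

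**What to change.** - **SAP 2.8.1.6, rates.** Keep n (%) and add, per window, the number of patients with a first event in that window per patient-year on LCI699. Censor time at that event and remove placebo time. A patient with an event in an earlier window is at risk again at the start of the next, as in the present n (%).
- **SAP 2.8.1.6, last window.** Split the time after Week 72 into 24-week blocks, continuing while "there are at least 15 patients available for the analysis at that time point", the SAP's existing rule for extension time points (2.1.1.10).
- **SAP 1 and 1.2.5.** Reconcile the 16-month and 4-month statements with each other and with protocol 4.1.5, 4.3 and 6.1.5.
- **SAP 2.8.4.2.** Restate the temperature rule as an absolute value, which 39.1 °C appears to be, with the sponsor confirming the threshold before tables are run.

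No new data are needed. The main cost is programming: SAP 2.4.1 derives only one overall LCI699 duration, with interruptions included, so exposure per window without placebo time must be derived. The rates assume a constant hazard within each window, which is weakest from Baseline to Week 26 because that window contains titration. The temperature change is one line.

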2.8.2 Deaths

Deaths will be reported, by primary system organ class and preferred term. Patients will not be followed-up for survival in this study, with patients considered to be off-treatment 30 days after treatment discontinuation.

2.8.3 Laboratory data

For analyzing laboratory results, data from all sources (central and local laboratories) will be combined. The summaries will include all laboratory assessments up to data cut-off date. All laboratory assessments will be listed. Results will be reported for each visit at which collected in the Core, Follow-up, and Extension Periods through the last study visit.

Eligible laboratory data will be classified into CTC grades according to NCI CTCAE v4.03. In the unlikely case a local laboratory normal range overlaps into the higher (i.e. non-zero) CTC grade, if the laboratory value is within local normal limits it will be assigned a CTC grade of zero.

The following summaries will be produced for the laboratory data (by laboratory parameter) for the overall study period:

- Number and percentage of patients with worst post-baseline CTC grade (regardless of the baseline status). Each patient will be counted only for the worst grade observed post-baseline
- Number and percentage of patients meeting categorical liver function test criteria, including Hy's Law criteria for liver injury (ALT or AST > 3 x ULN and TBIL ≥ 2 x ULN and ALP < 2 x ULN). Each patient will be counted only for the worst grade observed post-baseline
- Shift tables from baseline to the worst post-baseline value and from baseline to the last post-baseline values using CTC grades will be produced for hematology, biochemistry, and urine laboratory parameters with CTC grades
- For laboratory parameters in which CTC grades are not defined, shift tables from baseline to the worst post-baseline value and from baseline to the last post-baseline values will be produced using the low/normal/high classifications based on laboratory reference ranges
- Shift tables of fasting blood glucose and HbA1c from baseline to the highest post-baseline value and from baseline to the last post-baseline values using the ADA (2010) classification.
- Selected laboratory data will be also be displayed by presenting summary statistics of change from baseline value.

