2.1.1.9 AE summary cutoff

All data up to data cut-off date will be at least listed. All safety data prior to the data cut-off will be summarized with the exception of AEs and deaths, which will follow the cut-off rule specified below.

AE/death summary cut-off date = min { data cut-off date, max(last dosing date + 30 , safety follow-up visit date) }

AEs/deaths that occur after the AE/death summary cut-off date but prior to the data cut-off date will be listed and flagged.

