2.8 Safety analyses

The assessment of safety will be based mainly on the frequency of adverse events and on the number of laboratory values that fall outside the pre-determined ranges. Other safety data (e.g. electrocardiogram, vital signs, and special tests) will also be presented.

In the Final CSR results for the overall study period will be analyzed, using the SAS. Results will be presented by Randomized patients, Non-randomized patients and All patients.

The safety results for the Final CSR will focus solely on the safety of LCI699. Therefore scheduled safety assessments performed whilst on placebo, for patients randomized to placebo during the RW period, will not be included. Similarly, adverse events with a start date which corresponds to when a patient was receiving placebo will not be included in adverse event summaries.

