2.8.4 Other safety data

2.8.4.1 ECG and cardiac imaging data

Fridericia's formula (QTcF) will be used to calculate the heart rate-corrected QT interval (ms) based on the heart rate (HR bpm) and QT (ms) for centrally-read data. These calculated QTc values will be used in ECG summary tables and listings. The formula is as follows:

$$QTcF \text{ (in ms)} = QT / (RR)^{1/3}$$

The following analyses will be performed for variables PR, QRS, QT interval, heart rate, and QTcF (Fridericia's) for the overall study period:

- summary statistics at baseline, all post-baseline time points as well as corresponding change from baseline.

- For randomized withdrawal period: summary statistics at randomization, all time points within randomized withdrawal period as well as corresponding changes from randomization
- Listing of ECG data including all scheduled and unscheduled time points

No imputation of missing data will be performed.

The number and percentage of patients with notable ECG interval values will be summarized.

A newly occurring ECG finding is defined as an notable finding at post-baseline that is not present at baseline.

The notable criteria for PR are

- > 200 ms post-baseline and \leq 200 ms at baseline
- Increase > 25% compared to baseline to a post-baseline value > 200 ms

The notable criteria for QRS are

- > 110 ms post-baseline and \leq 110 ms at baseline
- Increase > 25% compared to baseline to a post-baseline value > 110 ms

The notable criteria for QT and QTcF are

- > 450 ms at any post-baseline and \leq 450 ms at baseline
- > 480 ms at any post-baseline and \leq 480 ms at baseline
- > 500 ms at any post-baseline and \leq 500 ms at baseline
- an increase from baseline > 30 ms at any post-baseline
- an increase from baseline > 60 ms at any post-baseline

The percentage of patients having notable ECG interval values is based on the total number of patients who are at risk for a specific category. For new abnormality post-baseline values, this is the number of patients with both baseline and post-baseline evaluations who are normal at baseline. For abnormal change from baseline, this is the number of patients with both baseline and post baseline evaluations. A subject with multiple occurrences of a newly occurring abnormality is counted only once per abnormality.

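### The Final CSR safety rule removes only scheduled on-placebo assessments, so unscheduled values taken on placebo can set a patient's worst value in tables meant to describe LCI699

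*SAP*

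**What the plan says.** SAP 2.8 sets the scope: "The safety results for the Final CSR will focus solely on the safety of LCI699". For assessments it then gives the working rule: "Therefore scheduled safety assessments performed whilst on placebo, for patients randomized to placebo during the RW period, will not be included". Adverse events get a different rule, based on date (2.8, repeated in 2.8.1.3): "Adverse events with a start date which corresponds to when a patient was receiving placebo will not be included in adverse event summaries".

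SAP 2.8.3 is wider. It says that "data from all sources (central and local laboratories) will be combined" and adds: "The summaries will include all laboratory assessments up to data cut-off date". From these data it builds tables of worst post-baseline CTC grade, categorical liver criteria, shifts from baseline to the worst value and to the last value, and shifts to the highest glucose and HbA1c. SAP 2.1.1.9 is equally broad: "All safety data prior to the data cut-off will be summarized with the exception of AEs and deaths".

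For ECGs, SAP 2.8.4.1 counts patients whose QT or QTcF crosses a notable limit at any post-baseline point. Among the overall-period analyses it also lists: "For randomized withdrawal period: summary statistics at randomization, all time points within randomized withdrawal period as well as corresponding changes from randomization".

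Final CSR safety results are shown for randomized, non-randomized and all patients. There is no separate placebo column.

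**The concern.** The stated purpose and the working rule do not match. The purpose is to describe LCI699. The rule leaves in any laboratory, ECG or vital-sign value taken at an unscheduled contact while the patient was on placebo, and the laboratory section then takes everything up to cut-off.

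This matters because several of the tables are extreme-value summaries. A single sample can fix a patient's entry for a parameter. Protocol 1.1.1 lists glucose intolerance among the manifestations of hypercortisolism. A raised glucose at an unscheduled visit after withdrawal to placebo could therefore appear as that patient's highest post-baseline glucose in a table headed as LCI699 safety. Because both randomized arms share one column, the table would not reveal it.

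**Working it through.** The plan gives no figure to reproduce. The check is a comparison of the rules, followed by simple arithmetic on the exposed group.

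**1. Exclusion rules by data type**

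- Adverse events (SAP 2.8, 2.8.1.3): dropped if they start while the patient is on placebo. Planned and unplanned contacts are treated alike.
- mUFC and metabolic parameters (SAP 2.7.3, 2.7.4): dropped for visits at which the patient received placebo.
- Dose summaries (SAP 2.4.1): dose levels while on placebo are left out.
- Laboratory, ECG and vital signs (SAP 2.8): dropped only if scheduled.

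Only the last rule depends on whether the assessment was planned.

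**2. Two ways to read 2.8 with 2.8.3**

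- If 2.8 governs as the parent section, scheduled on-placebo values go and unscheduled ones stay.
- If the sentence in 2.8.3 is applied literally, both stay.

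Neither reading yields LCI699-only summaries.

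**3. Can such values exist in the database?**

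Yes.

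- Unscheduled visits are allowed throughout randomized withdrawal for symptoms of high or low cortisol (Protocol 4.1.3.4, SAP 1.2.3).
- Urgent local testing is allowed when hypocortisolism is suspected (Protocol 6.3.1).
- Unscheduled local results go into the CRF (Protocol 9.4).
- Unscheduled 12-lead ECGs may be taken at any time (Protocol Table 7-9).

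**4. Does the protocol's on-treatment definition close the gap?**

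No. In Protocol 10.5.3.1 that period runs from the first dose of study medication to 30 days after the last, so it spans the placebo weeks. The same section does describe the overall-period analysis as covering time on LCI699, so the SAP wording is wider than the protocol's aim.

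**5. Which tables can change?**

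- Can change: worst CTC grade, liver criteria, shifts to the worst or highest value, notable QT/QTcF counts, and vital-sign shifts based on notable values. Each can change only for a parameter measured in the sample, and only if that value is the most extreme in the patient's whole post-baseline record.
- Generally unchanged: shifts from baseline to the last value, because most patients have later values on LCI699. The exception is a patient who leaves the study during Period 3.

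**6. Exposed group, from planned numbers (Protocol 10.8, SAP 3.1)**

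- Placebo arm: 33. Randomized: 2 × 33 = 66. Enrolled: 132.
- 33/66 = 50% of the randomized column; 33/132 = 25% of the all-patients column.
- Time on placebo: Week 26 to Week 34, at most 8 weeks.
- One altered patient moves the randomized column by 1/66 = 1.5 percentage points and the all-patients column by 1/132 = 0.8 points.

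The 50% and 25% are ceilings set by the design, not forecasts. The documents do not say how many unscheduled on-placebo samples there were.

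**7. Direction**

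Adding values to the set from which a worst is taken can leave a patient's entry unchanged or make it worse, but not better.

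**8. The ECG bullet**

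This is a different problem. It asks for summaries by time point within randomized withdrawal, where Protocol Table 7-2 schedules ECGs at Weeks 26, 28, 30, 32 and 34. For placebo patients these include the scheduled assessments that 2.8 says to leave out. Under the Final CSR grouping, the arms would be pooled.

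**The case against.** The best defence is intent. SAP 2.8 is the parent of 2.8.3 and 2.8.4, and it states the LCI699-only purpose outright. The sentence on all laboratory assessments mainly sets a cut-off, echoing 2.1.1.9. Read literally it would also restore the scheduled values that 2.8 removes, so it is weak evidence of a deliberate override. A careful programmer might apply the purpose. This argument stands as far as it goes, but it does not remove the explicit qualifier *scheduled*, which the adverse-event and efficacy rules lack.

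Other points limit the effect, and they stand:

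- A placebo value counts only if it is the worst in a record of up to 48 weeks plus the extension.
- Patients with mUFC above 1.5 × ULN, and at least two individual samples above that level, must leave randomized withdrawal and resume open-label LCI699 (Protocol 4.1.3.6). This shortens placebo exposure in those most likely to show returning disease.
- Shift tables start from a pre-treatment baseline in patients who needed mUFC above 1.5 × ULN at entry. Returning hypercortisolism need not register as a worsening.
- The documents reviewed require no chemistry or hematology panel at an unscheduled visit. That the retained values are the most abnormal ones is plausible, since the visits are prompted by symptoms, but it is not shown.
- The protocol plans withdrawal-period safety by arm, and the core-phase results were reported in an interim CSR under a separate SAP that is not available here. Placebo safety data are therefore not lost to the programme.

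**Conclusion.** The gap in the wording is real and minor. Followed as written, the SAP keeps unscheduled on-placebo laboratory, ECG and vital-sign values in summaries meant for LCI699, and one of them can determine a placebo-arm patient's worst-value entry. The likely direction is to overstate abnormalities on LCI699. The size is unknown. The conclusion rests on the SAP text and planned arm sizes; actual randomized numbers and counts of unscheduled samples are not given.

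A reader might infer more than the documents support:

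- **That each such sample alters every worst-grade and shift table.** It can affect only parameters measured in it, only if it is the extreme value, and generally not the baseline-to-last shifts.
- **That low potassium from returning disease would be counted against LCI699.** Protocol 1.1.1 does not list it as a manifestation of hypercortisolism, while Protocol 2.7 lists hypokalemia among the risks of LCI699 itself. Glucose is the supported example.
- **That Holter results are affected.** Protocol Table 7-9 schedules no Holter recording between Weeks 24 and 48.
- **That the ECG bullet is further evidence of the same gap.** It concerns summaries by time point, not unscheduled or worst values, and is a separate inconsistency with 2.8.

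**What to change.** 1. In SAP 2.8, delete *scheduled*. State that the LCI699 summaries exclude any laboratory, ECG or vital-sign value, scheduled or unscheduled, central or local, dated within the patient's placebo dosing interval.
2. State how values are attributed when they fall between the last placebo dose and resumption of LCI699, or just after resumption.
3. Cross-refer to this rule in 2.8.3 and 2.8.4, so that the all-assessments sentence is read subject to it.
4. Keep the excluded values in the listings, with a flag.
5. Separately, remove the withdrawal-period ECG bullet in 2.8.4.1 or restrict it to patients randomized to LCI699.

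The cost is a few sentences and one date filter. SAP 1.2.3 records that the study was unblinded at the core-phase database lock, so the placebo intervals can be identified. There is one small downside: a late effect of LCI699 first measured soon after the switch to placebo would appear only in the flagged listings.
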